Clinical Study Protocol

Investigational Product: Oral nicotine products Sponsor Protocol Code: BAT2119018 Protocol Version: 3.0 Date: 06 April 2020

STUDY TITLE

A multi-centre, randomised, cross-over, pharmacokinetic study of 8 oral nicotine products

Sponsor

British American Tobacco (Investments) Limited, [name].

Substantial amendment

Amendment No	Final version date
2.0	17 Feb 2020
3.0	06 Apr 2020

2 **PROTOCOL SYNOPSIS**

Study Title

A Multi-Centre, Randomised, Cross-over, Pharmacokinetic Study of 8 Oral Nicotine products

Sponsor Protocol Code: BAT2119018

Study period

Estimated date of first subject enrolled: May 2020

Estimated date of last subject completed: Aug 2020

Objectives

Primary objective(s)

To determine the kinetics of nicotine absorption into the blood of subjects using different variants of smokeless nicotine products and to compare the nicotine PK parameters between smokeless nicotine products.

Secondary objectives

To evaluate product subjective measures of the different smokeless nicotine products and to determine the amount of residual nicotine in the used pouches.

Endpoints

Primary endpoint

PK parameters C_{max} and AUC_{0-6h} of nicotine.

Secondary endpoints

Scores on the product subjective measures questionnaires and the amount of residual nicotine in the used pouches.

Number of subjects planned

36 healthy volunteers will be randomised at two centres in competitive recruitment manner with a minimum of 20% female subjects.

Main eligibility criteria

Healthy daily user of smokeless snus or modern oral nicotine products aged 19-55 years.

Study design

Multi-centre, randomised, pharmacokinetic, cross-over study.

Methodology

36 healthy volunteers will after screening, and a familiarisation visit when the highest dose product will be tested for tolerance, be randomised to dosing and PK sampling with 8 oral nicotine products during two 4.5 days clinic admission periods or one 8.5 days clinic admission period. After the discharge from the second period a telephone follow-up will be done within a week.

Investigational product, dosage and mode of administration

8 oral nicotine products:

- 1) Swedish Snus (pouch) Granit Vit Stark with 13 mg/pouch nicotine
- 2) Lyft (Commercial product), 4 mg/pouch
- 3) Lyft (Commercial product), 10 mg/pouch

- 4) Lyft non-commercial (alginate removed), 10 mg/pouch
- 5) Lyft non-commercial (benzoic acid added), 4 mg/pouch
- 6) Lyft non-commercial (benzoic acid added), 10 mg/pouch
- 7) Lyft non-commercial (citric acid added), 10 mg/pouch
- 8) Lyft non-commercial (benzoic acid added, sweet base), 10 mg/pouch

Duration of treatment

Each of the study products will be used for 60 minutes for PK sampling.

Duration of subjects' involvement in the study

The screening procedure will take place up to 28 days before the start of the one 8.5 days or two 4.5 days PK sampling admission periods followed by telephone follow-up within a week after discharge from the second session. The total duration for each subject is not expected to exceed 7 weeks.

Pharmacokinetic assessments

Blood samples for pharmacokinetic parameters will be analysed at pre-dose, 5, 10, 20, 40, 50, 60, 65, 75, 90, 120, 240 and 360 minutes relative to the start of the 60 min product administration.

Safety assessments

Safety assessments will include symptom-oriented physical examination, oral mucosa examination, vital signs, clinical laboratory tests, and AE monitoring.

Statistical methods

A sample size of 32 subjects completing all PK sampling is calculated as sufficient. To achieve this, a total of 36 subject will be randomised to PK sampling.

Version 3.0

4 LIST OF ABBREVIATIONS AND DEFINITION OF TERMS

Abbreviation or term	Explanation
ADR	Adverse Drug Reaction
AE	Adverse event
BAT	British American Tobacco
BMI	Body mass index
CNS	Central nervous system
CRF	Case report form
CRO	Contract Research Organisation/Clinical Research Organisation
EC	Ethics Committee
ECG	Electro-cardiogram
EFV	Erythrocyte volume fraction
GCP	Good clinical practice
GMP	Good manufacturing practice
IB	Investigator's Brochure
ICH	International conference on harmonization
ICFIWRS	Informed Consent Form
ICLIWINS	Interactive Web Response System
NSAID	Non-steroidal anti-inflammatory drug
РК	Pharmacokinetic
PRRP	Potentially Reduced Risk Products
SAE	Serious adverse event
SUSAR	Suspected unexpected serious adverse reaction
TEAE	Treatment emergent Adverse Event
UADR	Unexpected Adverse Drug Reaction

5 INTRODUCTION

Cigarette smoking is a leading cause of numerous human disorders including lung cancer, pulmonary disease and cardiovascular disease. Cigarette smoke is a complex and dynamic mixture of more than 6,500 identified chemical constituents, some of which have been identified as potential contributors to the disease-causing effects of cigarette smoke.

A number of companies, including British American Tobacco (BAT), are developing alternative tobacco and nicotine products that deliver nicotine to the user but do not burn tobacco. BAT use the term 'potentially reduced risk products' (PRRPs) to describe tobacco and nicotine products that, based on the available science, have been shown to be reduced-risk; are likely to be reduced-risk; or have the potential to be reduced-risk, in each case if switched to exclusively as compared to continuing to smoke cigarettes. PRRPs include the following categories: electronic cigarettes (e-cigarettes), tobacco heating products and smokeless oral products, such as snus.

Recently, oral nicotine products containing little or no tobacco (henceforth referred to as 'modern oral') have emerged on the market as potential alternatives to existing oral tobacco products. One such product is "Lyft", a smokeless, tobacco-free oral product which is white in colour and comes in pouches containing high-quality food-grade ingredients including naturally derived nicotine, water, eucalyptus and pine tree fibres, flavouring and sweeteners. Consumers place the pouch between their gum and upper lip, typically for up to 60 minutes. During use, nicotine and flavours are released and the nicotine is absorbed through the oral mucosa in the gum.

Chemical analysis and *in vitro* data conducted by the sponsor suggests that Lyft modern oral products demonstrate a lower toxicant profile and reduced biological response compared to traditional tobacco-containing snus products. Therefore, understanding the rate of nicotine uptake is key information required to further characterise these products as potential alternatives to cigarette smoking and traditional snus use.

BAT is currently developing non-tobacco containing smokeless products with nicotine and aim to understand how this category of products impact nicotine pharmacokinetics. Therefore, BAT would like to conduct a pharmacokinetic study, using smokeless products only to obtain human pharmacokinetic data to understand product efficacy at delivering nicotine, provide safety data, and inform product design.

The results of this study will answer a fundamental science question as to the nicotine pharmacokinetics of these modern oral products.

5.1 Rationale for study design

This study was designed to assess nicotine uptake for modern oral products in comparison to traditional tobacco containing Swedish snus to understand product efficacy at delivering nicotine, provide safety data and inform product design. A crossover design was chosen to minimise variability and the number of subjects needed for evaluation. Subjects will be randomised to study product sequences to minimise assignment bias. By necessity, the subjects will not be fully blinded due to the different visual appearances between the snus product and the seven oral nicotine products. This is not anticipated to impact the outcome of the study endpoints. The bioanalytical laboratory will be blinded.

As the purpose of this study is to assess nicotine uptake for modern oral products in comparison to traditional snus, 8 smokeless nicotine pouch products will be used in this study. Smokeless pouch users or loose snus users as well as dual users (smokers or e-cigarette users and smokeless pouch or loose snus users) will be recruited.

To avoid any carry-over effect, a wash-out of 12 hours is planned between product administrations. Given the expected half-life of nicotine (about 2 hours), this wash-out period is judged to be sufficient.

5.2 Risk / benefit analysis

5.2.1 Risk Assessment

Smokeless pouch products, such as Swedish-type snus, have been used extensively as consumer products for decades. "Lyft", a smokeless, tobacco-free oral product comes in pouches containing high-quality food-grade ingredients including naturally derived nicotine, water, eucalyptus and pine tree fibres, flavouring and sweeteners. The sole pharmacologically active ingredient of the smokeless oral tobacco pouches is nicotine. Generally, such products are associated with minor and infrequent acute adverse effects, predominantly headaches, nausea, dizziness and palpitations. Human experience with this product category demonstrates an absence of significant acute adverse effects in humans, in line with the preclinical British American Tobacco Lyft non-tobacco containing smokeless pouch specific assessment (Unpublished data).

These non-tobacco containing smokeless pouches are oral products that consumers place between their gum and upper lip to release nicotine and flavours. It is widely acknowledged that most of the harm associated with conventional cigarettes is caused by the toxicants in the smoke produced by the burning of tobacco. Non-tobacco containing oral smokeless pouches deliver nicotine to the user through the oral mucosa in the absence of both tobacco and combustion and are therefore hypothesised to be substantially less toxic than cigarette smoke due to reduced exposure to chemical toxicants. Analytical analysis of modern oral products has shown that levels of chemical toxicants are reduced compared to cigarette smoke. A representative non-tobacco containing smokeless pouch product had either lower or no detectable levels of 11 harmful or potentially harmful constituents typically found in cigarette smoke (Unpublished data).

To date, no epidemiological studies have been performed with modern oral products. However, multiple studies have evaluated smokeless tobacco products, including pouched products similar in style to modern oral products except for their inclusion of tobacco. Multiple evaluations have concluded that risks of adverse health impacts from using snus are up to 90% lower than from using cigarettes (Lee, 2011; Lee, 2013; Levy et al., 2004; RCP, 2007; SCHNEIR, 2008). As these smokeless non-tobacco oral products are used in a similar way to Swedish-type snus, which contain tobacco, it is hypothesised that users of Swedish-type snus that switch exclusively to non-tobacco containing oral smokeless pouches would be exposed to less toxicants and therefore a similar if not lower risk than Swedish-type snus. BAT tobacco and/or nicotine products are not suitable for use by pregnant or breastfeeding women. Therefore, females of childbearing potential may only be included in the present study if they consent to take appropriate measures to prevent pregnancy during the study.

Nicotine use can have side effects, but subjects included in the study will already be users of nicotine and tobacco products. During study product use, it is not expected that subjects would be exposed to nicotine levels higher than those they are usually exposed to during their daily consumption of nicotine and tobacco products. The duration of exposure for each product has been determined by the standard use of such products. Therefore, acute risks related to the product administration are anticipated to be low.

The best way to avoid the risks associated with tobacco products is not to use them at all.

Each nicotine product will meet the required quality standard applicable to marketed tobacco or nicotine products (as relevant).

The dose of nicotine administered in this study is not anticipated to induce any additional potential risk to the subjects who are already users of nicotine and tobacco products. The safety monitoring practices employed by this protocol (i.e. symptom-oriented physical examination, oral mucosa examination, vital signs, clinical laboratory assessments, and AE questioning) are adequate to protect the subjects' safety and should detect all expected treatment-emergent AEs (TEAEs).

5.2.2 Benefit Assessment

There will be no medical advantages as a result of using the study products. However, the subjects will undergo a medical examination, which may provide them with information on their state of health.

Subjects will be able to ask for advice to stop using tobacco / nicotine products and any subjects who are smokers will be provided with a smoking cessation helpline number and/or web address, e.g. https://www.slutarokalinjen.se/.

Understanding the rate of nicotine uptake is key information required to further characterise these products as potential alternatives to cigarette smoking and traditional snus use.

To date, there are no published data on the delivery of nicotine to human subjects from modern oral products. Therefore, the results of this study will answer a fundamental science question as to the nicotine pharmacokinetics of these modern oral products.

6 INVESTIGATOR(S) AND STUDY ADMINISTRATIVE STRUCTURE

The study will take place at two study centres, 1) CTC Clinical Trial Consultants AB, [name] and 2) The Skåne University Hospital, Clinical Studies Sweden – Forum South, Clinical Trial Unit, Lund, Sweden. The Country Coordinating Investigator is [name] at the CTC Unit.

A total of 36 subjects will be selected to participate in the study to complete with at least 32 subjects.

The CRO company IRW Consulting will provide Project Management, Data Management, Pharmacovigilance, Clinical Monitoring, Biostatistics and Medical Writing Services.

7 STUDY OBJECTIVES AND ENDPOINTS

7.1 **Primary objective(s)**

The primary objective of this study is to determine the kinetics of nicotine absorption into the blood of subjects using different variants of smokeless nicotine products and to compare the nicotine PK parameters between smokeless nicotine products.

7.2 Primary endpoint(s)

The primary study endpoints are the PK parameters C_{max} and AUC_{0-6h} of nicotine.

7.3 Secondary objectives and endpoints

The secondary objectives of this study are to evaluate product subjective measures of the different smokeless nicotine products and to determine the amount of residual nicotine in the used pouches.

Secondary endpoints are the scores on the product subjective measures questionnaires and the amount of residual nicotine in the used pouches.

7.4 Safety endpoints

The safety endpoints are the incidence of AEs/SAEs, vital sign abnormality assessments, clinical laboratory abnormality assessments, and symptom-oriented physical examination findings.

8 INVESTIGATIONAL PLAN

8.1 Overall study design and schedule of events

This is a two centre, randomised, non-blinded, 8-product, 8-period crossover, single dose pharmacokinetic study, in which 36 healthy male or female adult users of smokeless nicotine products (subjects who use pouched snus should regularly use pouch weights of 0.6 g and above, and at least 7.5 mg nicotine/pouch) will be randomised in competitive recruitment manner to receive one of the study products during each study period. The 8 periods of product use and sampling will be scheduled during two admission periods of 4.5 days each. There is also option for subjects to perform the product use and sampling in one 8.5 days admission period. For subjects choosing the one 8.5 admission option, they will come to the clinic on day 1 and will then receive the 8 products and undergo PK sampling on days 2-9 after which the subject is discharged. For subjects choosing the two admission periods of 4.5 days, they will come to the clinic on day 1 and will then receive 4 of the 8 products and undergo PK sampling on days 2-5 after which the subject is

discharged. Subjects will return for a second admission on day 8 with PK dosing and PK sampling of the remaining 4 products on days 9-12.

To minimise the risk of dropouts during the study, it will be accepted for subjects to be discharged during the 8.5-day admission period, or one or both of the planned 4.5-day admission periods, to return for re-admission and the remaining dosing and sampling at a later date. This option will only be used if absolutely necessary to avoid subjects to dropout of the study.

Subjects will be aged 19-55 inclusive and judged to be healthy by pre-study screening. Subjects must have been using smokeless oral nicotine products daily for at least 6 months and must not be trying to quit or planning on quitting during the study period. Product use status will be confirmed with a urinary cotinine level of ≥ 100 ng/ml at screening.

Subject eligibility for this study will be determined at the screening visit and eligible subjects will be admitted to the clinical research unit (CRU) at least 13 hours prior to the first product administration. The screening visit will take place up to 28 days prior to the first admission for product administration and PK sampling.

During or after the screening visit but prior to admission for the confinement period, the subjects will attend the clinic for a familiarisation session in which they will be given the highest nicotine strength product (Granit Vit Stark 13 mg/pouch). The purpose of this familiarisation session is to ensure the subject tolerates the product with the highest nicotine strength to avoid dropouts due to product intolerance during the PK sampling period. The subject will use the product in the same way they would normally use a smokeless snus product. There will be a 20 minutes duration of use of the product (from the time the subject places the product in their mouth until the time the subject removes the product from their mouth). Subjects who successfully complete this familiarisation session, i.e., those who are willing to use and show no intolerance to the test product, will be allowed to continue in the study. Subjects who already use Granit Vit Stark (13 mg nicotine/pouch) or snus of 13 mg nicotine/pouch or above do not need to attend the familiarisation session.

For each study period, subjects will abstain from all tobacco and nicotine usage for 12 hours prior to product administration. In addition, subjects will fast overnight (no food or drink except water), for a minimum of 8 hours prior to each product administration. In the morning of each study session, Subjects will receive a standardised light breakfast which will be consumed at least one hour before product administration. Subjects will then receive a single product for a fixed period of 60 minutes and undergo a 6-hour PK blood sample collection. For each study period, a total of 13 blood samples (4 mL per sample) will be collected for PK assessments. PK blood samples will be collected prior to product administration (-5 mins) and at 5, 10, 20, 40, 50, 60, 65, 75, 90, 120, 240 and 360 minutes following product administration.

Subjects are to be discharged from the clinic after the final 6-hour post-administration PK sample collection in each admission period following medical approval. However, they may be advised to stay at the clinical site for safety reasons, if judged necessary by the physician in charge. End of study procedures will be performed prior to discharge from the clinical site.

The duration of the clinical portion of this study per subject (excluding the screening period) is expected to be 10 days. The actual overall study duration may vary.

No later than one week after the last clinic visit a post-study follow-up will be performed, which will be conducted via a telephone call with the subjects. The follow-up call will

collect information on the status of any ongoing AEs at discharge and any new AEs experienced after discharge.

The schema of a typical study day is presented in Figure 1.

The schedule of events of the study is described in Table 1.

Study Session Schematic

Figure 1 – Study Session Schematic

Table 1 Schedule of events

Event	Screening	Familiarisation	Admission 1	PK Day 1	PK Day 2	PK Day 3	PK Day 4	Admission 2	PK Day 5	PK Day 6	PK Day 7	PK Day 8 ⁴	Post- study telephone f/u
Informed consent	Х												
Demographics	Х												
Medical history	X												
Smokeless product use history	Х												
Physical examination ¹	Х		х				х	Х				х	
Oral mucosa examination	X		x	Х	Х	Х	X	X	X	X	X	X	
Vital signs	х		х	х	х	х	х	Х	х	х	х	х	
ECG	Х												
Prev. and concom. medication	X		X	Х	Х	Х	X	X	Х	х	X	х	Х
Eligibility	х		х										
Product Familiarisation		Х											
Randomisation			Х										
Study Product administration				Х	X	х	X		х	х	X	X	
PK Blood sampling,				х	х	х	х		х	х	х	х	
Blood sampling, safety	x ²		x ³				x ³	x ³				x ³	
Compliance and product accountability check		х		Х	Х	Х	X	X	х	х	х	х	
Adverse Events		X	Х	х	Х	X	х	Х	х	х	х	Х	Х
Pregnancy test (female subjects)	x ⁵		X					х				x ⁵	

Event	Screening	Familiarisation	Admission 1	PK Day 1	PK Day 2	PK Day 3	PK Day 4	Admission 2	PK Day 5	PK Day 6	PK Day 7	PK Day 84	Post- study telephone f/u
Urine sampling with Drug Screening, including cotinine	X		X					X					
Alcohol screen	х		х					х					
Product subjective measures Questionnaires				X	X	Х	Х		Х	Х	Х	Х	

¹ A full physical examination will be performed at screening by a medically qualified and licensed individual. At admission to the site and at discharge, symptom-oriented physical examinations will be performed, if needed

² All laboratory tests specified in appendix 19.2

³Full Blood Count, Sodium, potassium, glucose, creatinine, bilirubin total, alanine aminotransferase and albumin.

⁴In the event of early termination of a subject from the study, the tests scheduled on Day 8 will be performed if possible.

⁵A serum pregnancy test will be collected at screening. In the event of a positive or unclear result from a urine pregnancy test, a serum pregnancy test will also be performed to confirm the result.

8.2 Selection of study population

Subjects who meet all the inclusion criteria and none of the exclusion criteria at the screening visit may be eligible for participation in this study. Continued eligibility will be assessed upon admission to the clinical site, prior to randomisation and the first study product administration.

Screening failures are defined as participants who consent to participate in the clinical study but are not subsequently randomly assigned to the study intervention or entered in the study.

This study will aim to recruit an equal split of males and females. A minimum of 20% females (6 out of 32) will be recruited. This is deemed acceptable based on the Sponsor's demographic data of 2991 Swedish snus users surveyed in 2019, where 81% were male and 19% were female.

A subject who withdraws or is withdrawn during the pre-study evaluations but before receiving the study product will not be considered as a drop-out and will not be included in the final database.

Standbys should be recruited and available to replace any subject who withdraws prior to the first product administration.

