8.4.5 Blood Volume Collected

The total volume of blood withdrawn will be up to 466 mL. A catheter will be used for PK sampling. The total blood collection may be higher if repeat blood samples are required for safety assessments.

A detailed breakdown of the approximated blood volume to be collected per subject is presented in Table 2.

	Male subject	Female subject		
Screening clinical laboratory tests	14 mL	14 mL		
Pre-PK period 1 serum pregnancy test:	-	3.5 mL		
	416 mL	416 mL		
PK blood samples:	(13 samples per period x 4 mL per sample x 8 periods)	(13 samples per period x 4 mL per sample x 8 periods)		
Safety tests during study	36 mL (4 samples of 9 ml each)	36 mL (4 samples of 9 ml each)		
Total blood collection:	466 mL	466 mL		

Table 2. Blood Volume Breakdown

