8.6.3.3 Safety Statistical Methodology

Descriptive statistics will be used to summarise AEs and safety results.
- 8.6.4 Statistical/analytical issues
- 8.6.4.1 Adjustments for covariates

Possible confounding factors are gender and age. SAP will describe the method of analysis in detail.

- 8.6.4.2 Handling of dropouts or missing data Any missing PK data will not be replaced.
- 8.6.4.3 Multi-centre studies Not applicable
- 8.6.4.4 Multiple comparison/multiplicity Multiple comparisons adjustment must be used during the statistical analysis. Details of comparisons and adjustments will be presented in the SAP.
- 8.6.4.5 Examination of subgroups Subgroups by age and gender will be analysed.
- 8.6.4.6 Interim analyses and data monitoring No interim analyses planned.
- 8.6.5 Analysis data sets

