8.6.8 Determination of sample size

8.6.8.1 Primary Analysis

Seven one-sided primary superiority comparisons (products 3 vs 2, 4 vs 3, 3 vs 6, 3 vs 7, 2 vs 5, 6 vs 7 and 8 vs 6; see Section 8.3.1 for product numbering) will be performed in this study which utilises an 8-product and 8-sequence Williams crossover design. A minimum of 32 subjects (4 subjects per sequence) will be needed to achieve a balanced design and a power of 0.848 with an alpha level of 0.00714. This will enable detecting a difference of 25% in the log scale with a correlation of 0.3 and an intrasubject CV of 0.3. A total of 36 subjects will thus be needed to be included, if an overall drop-out rate of 10% is assumed in the study.

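### Two figures for women do not follow from their own inputs: 6 of 32 is 18.75%, not the stated 20% minimum, and the female blood total of 466 mL omits the listed 3.5 mL pregnancy sample

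*Protocol*

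**What the plan says.** **Share of women.** Section 8.2 first aims for equal numbers of men and women, then sets a floor: "A minimum of 20% females (6 out of 32) will be recruited". It supports the floor with a sponsor survey of Swedish snus users "where 81% were male and 19% were female". The base of 32 matches the completers required in Section 8.6.8.1: "A minimum of 32 subjects (4 subjects per sequence) will be needed". The synopsis uses a different base and gives no count: "36 healthy volunteers will be randomised at two centres in competitive recruitment manner with a minimum of 20% female subjects". Section 8.6.4.5 adds: "Subgroups by age and gender will be analysed".

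**Blood volume.** Section 8.4.5 gives a ceiling: "The total volume of blood withdrawn will be up to 466 mL". It allows a larger total where safety samples have to be repeated, and it describes the breakdown in Table 2 as approximate. Table 2 has a male and a female column. Both carry 14 mL on the row "Screening clinical laboratory tests", 416 mL of PK blood and 36 mL of safety samples. Only the female column has an entry, 3.5 mL, on the row "Pre-PK period 1 serum pregnancy test". Both columns end in 466 mL. Footnote 5 to Table 1 places the serum pregnancy test at screening, with a further serum test only to confirm a positive or unclear urine result.

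**The concern.** In Section 8.2 a percentage and a count stand in one sentence as the same minimum, and they differ. A minimum cannot be met by rounding down. The base also changes between the synopsis and Section 8.2, so the protocol can be read as setting a floor of 6, 7 or 8 women. Someone checking enrolment could count six women as compliant under the parenthesis and as a shortfall under the percentage. The floor also fixes the smallest possible size of the female group in the planned gender subgroup.

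In Table 2 two columns with different entries have the same total. The female total, and therefore the stated ceiling, appears to have been taken from the male column. At stake is whether the protocol states the planned blood draw correctly for women.

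**Working it through.** **Share of women**

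Inputs: 20% minimum and 6 of 32 (Section 8.2); 36 randomised (synopsis); 19% women in the survey (Section 8.2).

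1. How 6 can arise: 0.20 × 32 = 6.4, which gives 6 if rounded down or to the nearest whole number. The survey share also leads there: 0.19 × 32 = 6.08. Neither route makes 6 satisfy a 20% minimum.
2. The printed count as a share: 6 / 32 = 18.75%, below 20%. On the synopsis base, 6 / 36 = 16.7%.
3. The smallest compliant count is 0.20 × N rounded up:

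| Base N | 0.20 × N | Minimum count | Share at that count | Shortfall of 6 |
|---|---|---|---|---|
| 32 | 6.4 | 7 | 7 / 32 = 21.9% | 1 |
| 36 | 7.2 | 8 | 8 / 36 = 22.2% | 2 |

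4. The two counts are not interchangeable: 7 / 36 = 19.4%, which again misses 20%. The base has to be settled before the count.

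**Blood volume (Table 2)**

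1. PK blood: 13 samples × 4 mL × 8 periods = 416 mL. This reproduces the printed entry.
2. Safety samples: 4 × 9 mL = 36 mL. This also reproduces.
3. Male column: 14 + 416 + 36 = 466 mL. This reproduces the printed total.
4. Female column: 14 + 3.5 + 416 + 36 = 469.5 mL. The printed total is 466 mL.
5. Difference: 469.5 − 466 = 3.5 mL, and 3.5 / 466 = 0.75%.

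The printed female total is recovered only by leaving out the pregnancy row.

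**The case against.** **The rule is the percentage, and the count is only a gloss.** The aim is an equal split, the synopsis gives no count, and 18.75% is close to the survey's 19%. It is true that no section makes six a stopping rule or an enrolment limit. A reader might infer that sites will recruit to six and stop; the documents do not say so, and the floor may never bind. What remains is that the sentence contradicts itself and that the base differs between two sections.

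**Too few women to cover the sequences.** A reader might infer that six women damage the gender subgroup because at least two of the eight sequences would then contain no woman. The documents do not support building on this. Each woman is planned to receive all eight products, so a within-woman comparison does not need a woman in every sequence. No stratification by sex is described. Nor would eight women cure it: if allocation is independent of sex and sequences are as balanced as possible, the chance of one woman in each sequence is 4^8 / C(32,8) = 0.6% with 32 subjects, or 5^4 × 4^4 / C(36,8) = 0.5% with 36. The reason to correct the count is the stated minimum, not sequence coverage.

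**The blood table is approximate and the gap is trivial.** The gap is indeed trivial, and no eligibility, stopping or safety rule is tied to 466 mL. A reader might infer a safety problem; the documents give no basis for one. However, approximation does not explain two columns with different entries and the same total, and the allowance for repeat samples does not cover a row listed as planned.

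**The 3.5 mL may not be additional.** It could already lie within the 14 mL screening draw, since Table 1 places the serum test at screening. The text of Appendix 19.2 available to me does not show the laboratory list, so this cannot be settled. Against it, men have the same 14 mL and no pregnancy test, and Table 2 lists the sample on its own row. This point stands to the extent that 469.5 mL must be stated conditionally.

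**Conclusion.** Both figures are wrong as written.

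- **Minimum of women:** six of 32 is 18.75% and does not meet a 20% minimum. The compliant count is 7 on a base of 32 or 8 on a base of 36, so the printed count is short by one or two women. This rests only on the protocol's own numbers and on reading a minimum as a minimum.
- **Blood volume:** the entries in the female column sum to 469.5 mL against a printed 466 mL, a gap of 3.5 mL (0.75%). That 469.5 mL is the correct total assumes that the serum pregnancy row is a sample additional to the screening draw. If it is not, the separate row is what needs correcting. Either way, row and total disagree.

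Both are minor. They do not affect the sample size, the power or the primary comparisons of Cmax and AUC0-6h. They merit correction because one is an enrolment floor and the other a stated maximum, and both can be put right at almost no cost.

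**What to change.** 1. Use one base for the 20% in the synopsis and Section 8.2, and print the count that meets it: at least 8 if the base is the 36 randomised, at least 7 if it is 32. The count should be a recruitment floor, as both sections now word it. A floor on completers could not be enforced at randomisation, because completion is known only later.
2. Reconcile the serum pregnancy-test row of Table 2 with footnote 5 of Table 1 on when the sample is taken and whether it is separate from the 14 mL screening draw. Then restate the female total and the ceiling in Section 8.4.5. Both become 469.5 mL if the sample is additional; the male total stays at 466 mL.

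The cost is a wording change in three places (the synopsis, Section 8.2, and Section 8.4.5 with Table 2) and, if the floor binds, one or two more women within the same 36. In a user population that is 81% male by the sponsor's survey, that could slow recruitment slightly. No change to the design or the analysis is needed.
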